4.3 Schedule of Events

	Screening /Enrollment (-60 days of procedure)	Procedure	6 weeks (± 7 days)	3 months (± 14 days)	6 months (± 14 days)	12 months (± 30 days)	24 months (± 60 days)
Informed consent	X						
Medical History	X						
Demographics	X						
Concomitant medications review	X	X	X	X	X	X	X**
Oswestry Disability Index v2.1a	X		X	X	X	X	X**
Visual Analog Scale (VAS) back and leg	X		X	X	X	X	X**
Radiographic X-rays (AP/ Lateral with Flexion and Extension)	X		X	X	X	X	X**
CT Scan						X*	
Urine Pregnancy Test						X*	
AE/ SAE review	X	X	X	X	X	X	X**
*CT scan & Urine Pregnancy Test not standard of care. Cost will be covered by study sponsor.							
** Optional time point (when available)							

4.5 Fusion Determination

Fusion will be assessed by an independent radiologist using the subjects' 12 month visit CT images. The extent of fusion will be determined using the Lenke classification. The scale is as follows:

- Grade A - Definitely solid with bilateral trabeculated stout fusion masses present
- Grade B - Possibly solid with a unilateral large fusion mass and a contralateral small fusion mass
- Grade C - Probably not solid with a small fusion mass bilaterally
- Grade D - Definitely not solid with bone graft resorption or obvious pseudoarthrosis bilaterally

Radiographic success: radiographic success is defined as grade A.

Partial radiographic success: partial radiographic success is defined as grade B. Images graded as "B" will be subcategorized by the location of the unilateral large fusion mass (autograft side, B-a vs. ViviGen side, B-v).

Radiographic Failure: radiographic failure is defined as grades C or D.

4.6 Success Criteria

4.6.1 Primary Objective

A subject outcome will be considered a success if fusion is graded as a Grade A. A subject outcome will be considered a partial success if fusion is graded as a Grade B. Images graded as "B" will be subcategorized by the location of the unilateral large fusion mass (autograft side, B-a vs. ViviGen side, B-v).

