4.2 Surgical Procedure

After receiving antibiotic prophylaxis, the patient is placed under general anesthesia and positioned prone. A midline posterior approach is performed, exposing the posterior lumbar elements including the facet joints. Polyaxial pedicle screws are placed bilaterally, using fluoroscopic guidance, depending on preference of the surgeon.

In cases of neurogenic claudication related to spinal canal stenosis, the central part of the spinal canal is decompressed by laminectomy. In cases of radicular leg pain related to foraminal stenosis, partial facetectomies will be performed as needed to decompress the associated nerve roots.

Titanium rods are then positioned interconnecting the screws on each side. The posterolateral cortical bony surfaces are then fully decorticated and supplemented with milled local autograft bone on one side and an equal volume of Depuy Synthes ViviGen on the other side.

Data will be collected during and immediately after the surgery according to the parameters described by the ViviGen Lumbar study CRFs. This includes: diagnosis, duration of surgery, blood loss, OR time, length of hospital stay, instrumentation used, type of procedure, and surgical level(s). In addition, all intraoperative complications (e.g. excessive blood loss, hematoma, vascular injury, etc.) will be reported and recorded as a complication in the study CRFs.

Intra-operative (after hardware installation is completed) and immediate post-operative x-rays will be obtained. Postoperative care will follow the standard of care for subjects who undergo fusion procedures.

Postoperative care is extremely important. The subjects will be warned that noncompliance with postoperative instructions could lead to breakage of the pedicle screw system requiring revision surgery.

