5 STATISTICAL ANALYSIS PLAN

Statistical analyses will be performed as deemed appropriate to evaluate different healing outcomes across the various patient populations.

Primary outcome analysis to assess the final fusion status of all enrolled patients will be performed prospectively by the former principal investigator, Dr. [name]. Following his departure from The Ohio State University, the investigator(s) will review the 12 month CT scans to evaluate each subject for radiographic success, partial success, or failure.

In case early findings reveal a statistical difference in fusion grades comparing the sides of autograft and ViviGen Cellular Bone matrix, enrollment will cease as investigators are unlikely to maintain clinical equipoise. Similarly, if the analysis suggests it is unlikely the study will achieve statistical significance, the investigators may choose to close the trial early for futility. Currently enrolled subjects will be followed throughout the remainder of the study, up to 12 months post-surgery.

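### The side comparison that can end enrollment rests on one bilateral Lenke grade, which has no clear place for a large fusion mass opposite resorption or pseudoarthrosis and no stated paired analysis

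*Combined protocol and SAP*

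**What the plan says.** Section 4.2 sets up a within-patient contrast: the decorticated surfaces are "supplemented with milled local autograft bone on one side and an equal volume of Depuy Synthes ViviGen on the other side".

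Sections 4.5 and 4.6.1 record fusion from the 12-month CT as one Lenke grade per subject. Grade A requires stout masses on both sides, and "A subject outcome will be considered a success if fusion is graded as a Grade A". The next grade reads "Grade B - Possibly solid with a unilateral large fusion mass and a contralateral small fusion mass". It counts as partial success and is "subcategorized by the location of the unilateral large fusion mass (autograft side, B-a vs. ViviGen side, B-v". Grade C is a small mass on both sides. Grade D is "Definitely not solid with bone graft resorption or obvious pseudoarthrosis bilaterally". Finally, "radiographic failure is defined as grades C or D".

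Section 5 makes the contrast between sides consequential. If early findings show a "statistical difference in fusion grades comparing the sides of autograft and ViviGen Cellular Bone matrix, enrollment will cease". It defines no grade for each side, paired test, alpha or schedule of looks for this. On method it says only "Statistical analyses will be performed as deemed appropriate".

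**The concern.** A comparison of two grafts within a patient needs a result for each side. The plan supplies a subject-level grade plus a side code that exists only inside Grade B. The code is therefore complete only if every patient with one clearly better side lands in B. As worded, B requires a small mass on the weaker side, so a patient whose weaker side has resorbed or formed a pseudoarthrosis may not qualify. Such a patient carries the strongest evidence of a difference between grafts.

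Two quantities are at stake. One is the side comparison that can end enrollment. The other is any ViviGen-side fusion rate read from the recorded grades as A + B-v. Once a patient is recorded as D, the recorded grade no longer shows which side was solid, and only re-reading the scan would recover it.

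**Working it through.** **Step 1. Map the side states to the grades.** Call each side large (L; stout or large mass, taken here as solid), small (S), or resorbed/pseudoarthrosis (R). With the wording of Section 4.5 read strictly:

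| ViviGen side | Autograft L | Autograft S | Autograft R |
|---|---|---|---|
| L | A | B-v | no clear grade |
| S | B-a | C | no clear grade |
| R | no clear grade | no clear grade | D |

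Five of the nine states have a grade. For those five, the record shows which side did better or that they tied. Four have none: L opposite R and S opposite R, each in both directions. S opposite R is not solid on either side, so it does not affect a solid/not-solid comparison. It would matter if ordered grades were compared.

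**Step 2. Check the other reading of D.** The word bilaterally might modify only pseudoarthrosis. One-sided resorption could then be graded D. A patient with a large mass on the other side would then be called definitely not solid and would carry no side code.

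**Step 3. Illustrate the size.** The plan has no figure to reproduce, because it states no rate, sample size, alpha or test. The following are assumptions:

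- Side probabilities L/S/R: ViviGen 0.75/0.15/0.10, autograft 0.55/0.25/0.20. The true difference is 0.75 - 0.55 = 0.20.
- Joint cells from a bivariate normal latent variable cut at these margins, correlation 0, 0.3, 0.5 or 0.7.
- f = share of L-opposite-R patients placed outside B.
- N = 100, one two-sided exact McNemar test at 5% on B-v against B-a, with power summed over the binomial number of discordant pairs. This test is a reconstruction.

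With the ViviGen side written first:

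- B-v = LS + (1 - f) x LR
- B-a = SL + (1 - f) x RL
- A + B-v understates the ViviGen-side rate by f x LR

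At correlation 0:

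- LS = 0.75 x 0.25 = 0.1875 and LR = 0.75 x 0.20 = 0.150
- SL = 0.15 x 0.55 = 0.0825 and RL = 0.10 x 0.55 = 0.055
- f = 0: 0.3375 - 0.1375 = 0.200
- f = 0.5: 0.2625 - 0.1100 = 0.1525
- f = 1: 0.1875 - 0.0825 = 0.105

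| Correlation | 0 | 0.3 | 0.5 | 0.7 |
|---|---|---|---|---|
| Recorded difference, f = 0.5 (points) | 15.3 | 15.6 | 16.1 | 16.8 |
| Recorded difference, f = 1 (points) | 10.5 | 11.3 | 12.2 | 13.7 |
| Power, side grades (same as f = 0) | 81% | 88% | 93% | 97% |
| Power, f = 0.5 | 66% | 76% | 84% | 93% |
| Power, f = 1 | 45% | 57% | 69% | 85% |

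**Step 4. Equal sides.** With 0.60/0.25/0.15 on both sides, LR at correlation 0 is 0.60 x 0.15 = 0.09. Over the four correlations, A + B-v understates ViviGen-side fusion by 9, 6, 4 and 2 points at f = 1, and by half of that at f = 0.5. B-v minus B-a stays unbiased, because the losses on the two sides cancel.

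**The case against.** **The side code already exists.** A reader might infer that the plan has no side information, or cannot show which graft did better. The documents do not support that. For patients who fit the scale, A, C and D are ties and B-a/B-v orders the sides, so a paired test could be run on the recorded data. What stands is that no such test is planned, and that the code covers only patients placed in B.

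**The primary outcome is legitimate.** A reader might take Grade A success as the error. Section 1.1 is about outcomes in patients and Section 3.1 calls the study single-arm, so a bilateral patient-level grade suits the stated aim. The gap lies in Section 4.5's grade wording and Section 5's undefined comparison.

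**The reader may simply use B.** The sub-code turns on where the single large mass lies, so a reader could put these patients in B without strain. The loss is then zero. The documents do not say which choice is made. The reading form is not among them, so it may already have side fields.

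**The figures are assumed.** This stands in full. They also describe one fixed test, whereas Section 5 acts on early findings, so they do not measure the stopping rule itself. A reader might further infer that the gap creates a false difference between equal grafts. That would need the two grafts to fail in different ways, which nothing in the documents suggests.

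**Conclusion.** The point holds as a gap in wording and specification. ViviGen is on one side under Section 4.2, the side result is recorded only within Grade B, one-sided resorption or pseudoarthrosis has no clear grade, and the comparison that can end enrollment has no side-level endpoint or paired analysis. Confidence in that is high.

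Confidence does not extend to the size. The cost runs from nothing, if every large-opposite-resorbed patient goes to B, to a fall in power from 81% to 45% at correlation 0 (97% to 85% at 0.7) if all fall outside B. Both ends rest on the assumed rates, N = 100, a large mass counting as solid (Section 4.5 calls Grade B only possibly solid), and a single fixed test. This should be fixed because the repair is cheap and protects the comparison on which the plan proposes to act.

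**What to change.** - **Record each side.** On the same 12-month CT and with the same reader, grade each side as solid, small mass, or resorbed/pseudoarthrosis. Section 3.1 allows several levels, so state in advance how levels combine into one result per side.
- **Name the analysis.** Report the ViviGen-side fusion proportion with a 95% CI and the paired difference from the autograft side (exact McNemar with CI). Make this the comparison used in Section 5, with its alpha and timing of looks stated.
- **Keep the subject-level Lenke grade** as the patient-level outcome, and state where one-sided resorption or pseudoarthrosis is placed.
- **Reconcile two pairs of sections.** Section 4.5 (independent radiologist) and Section 5 (former principal investigator, then the investigators) differ on who reads the CT. Section 2.2 (the posterolateral gutters, with no mention of a side) and Section 4.2 (one side) differ on where ViviGen is placed.

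The cost is protocol and SAP wording and a slightly longer reading form, with no extra scan, patient or reader. If any CTs have already been graded, which the documents do not state, they need re-reading, and the side-level outcome should be labelled as added after those readings.

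### No stated outcome category isolates ViviGen: B-a and B-v are both partial success, and the recorded side code is not used in any outcome

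*Combined protocol and SAP*

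**What the plan says.** Under section 4.2, the decorticated bone is "supplemented with milled local autograft bone on one side and an equal volume of Depuy Synthes ViviGen on the other side". Each subject therefore carries both grafts.

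Section 4.5 grades the 12-month CT on four levels. The top level is "Grade A - Definitely solid with bilateral trabeculated stout fusion masses present". Grade B is "Possibly solid with a unilateral large fusion mass and a contralateral small fusion mass". Grades C and D describe poor results on both sides, and "Radiographic Failure: radiographic failure is defined as grades C or D".

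Section 4.6.1 turns the grades into the primary outcome: "A subject outcome will be considered a success if fusion is graded as a Grade A", and "A subject outcome will be considered a partial success if fusion is graded as a Grade B". Grade B images are also "subcategorized by the location of the unilateral large fusion mass (autograft side, B-a vs. ViviGen side, B-v").

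Section 5 has the 12-month scans read to "evaluate each subject for radiographic success, partial success, or failure". It also says that enrollment will stop if early findings show a statistical difference between the autograft and ViviGen sides. It names no test for that comparison and no final analysis that uses the side code. The choice of analyses is otherwise left open.

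**The concern.** Section 3.1 describes the study as assessing fusion with ViviGen. The split-side surgery and the B-a/B-v code show that the plan wants to know which graft produced the bone. The outcome rule, however, takes only the overall grade as its input. B-a is a poor ViviGen result beside a good autograft result, and B-v is the opposite, yet both get the same label. A subject with a large autograft mass and a small ViviGen mass can never be a failure, because failure requires both sides to do poorly.

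The interpretation of the trial is at stake. Partial-success and failure rates reported as planned reflect the autograft as well as ViviGen, and a reader cannot separate the two from the three categories. Because section 5 does not fix how the side code will be used, splitting or pooling Grade B could be decided after the results are known.

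**Working it through.** The plan states no fusion rate, sample size or target, so it has no figure to reproduce. The check enumerates the grades.

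**Inputs**
- Grade definitions and the success, partial-success and failure rule: sections 4.5 and 4.6.1.
- One graft per side: section 4.2.
- *pa* and *pv*, the probabilities of a large mass on the autograft and ViviGen sides: not in the documents, so assumed and varied.
- Any side without a large mass shows a small mass: assumed, and relaxed in step 4.

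**1. Grades as a function of the two sides.** With independent sides:
- A = pa × pv
- B-a = pa × (1 − pv)
- B-v = (1 − pa) × pv
- C or D = (1 − pa) × (1 − pv)

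Partial success = B-a + B-v = pa + pv × (1 − 2pa).

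**2. ViviGen never forms a large mass (pv = 0).** Then A = 0, B-v = 0, partial success = pa and failure = 1 − pa. This case needs no independence assumption.

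| pa | Success | Partial success | Failure | ViviGen side poor |
|---|---|---|---|---|
| 0.3 | 0% | 30% | 70% | 100% |
| 0.5 | 0% | 50% | 50% | 100% |
| 0.8 | 0% | 80% | 20% | 100% |
| 0.9 | 0% | 90% | 10% | 100% |

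Partial success exceeds half only if pa exceeds 0.5.

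**3. ViviGen works sometimes.**
- Independent sides, pa = 0.8, pv = 0.3: A = 0.8 × 0.3 = 24%; B-a = 0.8 × 0.7 = 56%; B-v = 0.2 × 0.3 = 6%; C or D = 0.2 × 0.7 = 14%. Partial success is 56 + 6 = 62%, and most of it is B-a. Failure is 14%, while the ViviGen side did poorly in 70%.
- Correlated sides, pa = 0.8, pv = 0.6: P(A) can lie between 0.8 + 0.6 − 1 = 0.40 and 0.60. Failure = 1 − 0.8 − 0.6 + P(A), which is 0% to 20%. Partial success = 0.8 + 0.6 − 2 × P(A), which is 60% to 20%. The ViviGen side did poorly in 40% throughout.

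**4. Relaxing the small-mass assumption.** Let *s* be the chance that a poor ViviGen side opposite a large autograft mass shows the small mass that Grade B requires. With pv = 0, partial success = pa × s. At s = 0.75 it exceeds half only if pa > 0.5 / 0.75 = 0.667. At s = 0.5 it cannot exceed half, and at pa = 0.9 it is 45%. The remaining subjects, with a large mass opposite a resorbed side, fit no listed grade, because C and D are both bilateral.

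**5. The side-specific alternative.** P(A) + P(B-v) is the probability of a large mass on the ViviGen side. It equals pv whatever the correlation between sides, provided the unlisted combination in step 4 is coded by side and each subject has one grade. In the example of step 3 with independent sides, 24% + 6% = 30% = pv.

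**The case against.** The best defence is that the outcome is meant to describe the subject. Success is Grade A alone, and that is 0% when ViviGen never forms a large mass, whatever the autograft does. Partial success is kept apart from success. The side code is written into the primary objective, so A, B-a, B-v and C/D can all be counted later. All of this stands, and it limits the point. But partial success is kept apart from failure too, so B-a ranks above failure because of the autograft side. Recording a code also does not prespecify its use.

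A reader might infer several stronger things that the documents do not support:

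- **ViviGen is credited in most subjects even if it never works.** No autograft rate is given. The statement needs a rate above 0.5, or higher if some ViviGen sides show no small mass. The plan also never says that partial success counts as success or that A and B are pooled.
- **Partial success and failure cannot tell a working ViviGen graft from an inert one.** With independent sides, failure falls from 1 − pa to 0 as pv goes from 0 to 1. At pa = 0.8, partial success moves from 80% to 20%. It is flat only at exactly pa = 0.5. Its fall when pa is above 0.5 includes subjects moving up to Grade A, which is not a defect.
- **Section 5 ignores the sides.** It does compare them, but only as a trigger to stop enrollment.
- **In B-a only the autograft side fused.** Grade B is a possibly solid result with a small mass opposite, so the code shows where the large mass is and does not establish fusion on one side only.

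A fair caution about the remedy is that B-v is itself only possibly solid. A or B-v should therefore be described as a large mass on the ViviGen side and not as full fusion success.

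**Conclusion.** The concern holds in a limited form. B-a and B-v receive the same subject-level label, failure requires both sides to do poorly, and no stated outcome category isolates ViviGen. Grade A depends on both sides, and the other two categories mix in the autograft result.

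The size depends on rates that the plan does not give. In the illustration with pa = 0.8 and pv = 0, the reported failure rate is 20% against a poor ViviGen side in 100%. With pa = 0.8 and pv = 0.6 it is 0% to 20% against 40%, depending on the correlation between sides. Both assume that a poor side shows a small mass and that each subject has one grade. The qualitative point rests only on the grade definitions. The change should be made, because the information is already collected and only its use is unspecified.

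**What to change.** - Keep Grade A / B / C-D as the procedure-level outcome.
- In sections 4.5, 4.6.1 and 5, add a prespecified ViviGen-side result: large fusion mass on the ViviGen side achieved = Grade A or B-v; not achieved = Grade B-a, C or D. Report the proportion with an exact 95% confidence interval.
- Report B-a and B-v separately. State that pooled Grade B, or A plus B, will not be presented as evidence for ViviGen.
- State how two cases are coded for this result: multilevel subjects (allowed by sections 3.1 and 3.2) whose levels differ in grade, for example B-a at one level and B-v at another; and a large mass opposite a resorbed side.

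The cost is wording in three sections, two coding rules and one extra proportion from codes already recorded. It needs no additional images or subjects. The small downside is that this proportion may look less favourable to ViviGen than success plus partial success.

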4.6.2 Secondary Objectives

The secondary measures of effectiveness will be determined by maintenance or improvement of pain and disability scores from completed questionnaires (VAS and ODI v2.1a)

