3 TRIAL DESIGN

3.1 Design

This is a prospective, single-arm post market study of patients to assess fusion in one or multiple continuous levels of the lumbosacral spine (L1-S1) using ViviGen Cellular Bone Matrix. All subjects will be followed up to 24 months for final assessment.

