3.2 Inclusion Criteria

Subjects will be considered for inclusion in this trial if they satisfy the following criteria.

1. Subject is scheduled to undergo a single or multilevel posterolateral spinal fusion surgery using ViviGen Cellular Bone matrix.
2. Subject must be over the age of 18 years old.
3. Subject has been unresponsive to conservative care for a minimum of 6 months.
4. The subject must in the investigator's opinion, be psychosocially, mentally, and physically able to fully comply with this protocol including the required follow-up visits, the filling out of required forms, and have the ability to understand and give written informed consent.

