4.1.3 Clinical Assessments

Subject study data will be collected preoperatively, intra-operatively and postoperatively at 6 weeks as well as 3, 6, 12 and when available, 24 months. The following data will be recorded on the Case Report Forms (CRFs) and in addition, electronic data entry will be employed via an Internet connection when possible using an Electronic Data Capture (EDC) system, REDCap.

Oswestry Disability Index v2.1a (ODI): Pre-operatively the subject will complete the Oswestry Disability Index v2.1a for baseline low back pain and functional assessment. The questionnaire is a combined pain and function index which will be used to assess the subject's back pain and how that pain affects the subject's ability to manage in everyday life. The questionnaire is divided into ten sections designed to assess limitations of various activities of daily living. Each section contains six statements and each statement describes a greater degree of difficulty in that activity than the preceding statement. The subject marks the one statement in each section, which describes his/her limitations most accurately. Each section is scored on a 0-5 scale, 5 representing the greatest disability. The scores for all sections are added together, giving a possible score of 50. The total is doubled and expressed as a percentage. If a subject marks two statements, the highest scoring

statement is recorded as a true indication of his disability. If a section is not completed because it is inapplicable, the final score is adjusted to obtain a percentage.

Back and Radicular Leg Pain: Preoperatively all subjects will assess their back and/or radicular leg pain in one or both legs using a visual analog scale (VAS) from 0-10 with 10 being considered most painful.

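### Section 4.6.2 counts an unchanged VAS or ODI score as secondary effectiveness and leaves the unit, deciding visit and combination of scales undefined

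*Combined protocol and SAP*

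**What the plan says.** Section 4.6.2 bases the secondary measures of effectiveness on "maintenance or improvement of pain and disability scores from completed questionnaires", naming VAS and ODI v2.1a. It gives no minimum change, deciding visit, unit of judgement, rule for combining scales or benchmark rate. Section 5 describes no analysis of either instrument.

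The primary objective in section 4.6.1 is worded by subject: "A subject outcome will be considered a success if fusion is graded as a Grade A". Section 4.6.2 has no equivalent sentence.

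Three other parts of the protocol bear on the point:

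- **Population.** Section 3.2 requires that "Subject has been unresponsive to conservative care for a minimum of 6 months". Section 2.1 explains fusion by the expectation that stopping motion will improve both pain and disability.
- **Design.** Section 3.1 states: "This is a prospective, single-arm post market study of patients to assess fusion". Under section 4.2 each subject receives autograft on one side and ViviGen on the other, so patient-level VAS and ODI have no comparator, either between or within subjects.
- **Measurement.** Section 4.1.3 has subjects rate "back and/or radicular leg pain in one or both legs" before surgery on a "visual analog scale (VAS) from 0-10 with 10 being considered most painful". For ODI, "Pre-operatively the subject will complete the Oswestry Disability Index v2.1a for baseline low back pain and functional assessment". Sections 4.3 and 4.4 repeat both instruments at 6 weeks and 3, 6 and 12 months, with 24 months optional.

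**The concern.** For someone operated on because conservative care failed, the same pain a year later means that the improvement foreseen in section 2.1 did not occur. Section 4.6.2 would still count that as effectiveness. With no threshold, benchmark or control, a percentage maintained or improved has nothing to be read against, and a substantial percentage is expected by chance alone.

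The missing definitions make this worse. The same data could be summarised per subject or by group mean, scale by scale or combined, at any visit, and each choice has a different no-benefit rate.

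Leg pain adds a further difficulty. The and/or wording suggests that some subjects may have no leg pain before surgery. If they are recorded as 0, they cannot improve and meet the criterion unless new pain appears.

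**Working it through.** The documents state no sample size, SD, expected rate or alpha for VAS or ODI, so there is no planned figure to reproduce. The check asks how often the criterion would be met if nothing changed on average.

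**Inputs from the protocol.** VAS runs from 0 to 10, higher is worse, and its recording resolution is not stated. ODI has ten sections scored 0 to 5, and "The total is doubled and expressed as a percentage", so it moves in steps of 2 when all sections are answered.

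**Assumed inputs.** Normally distributed change with true mean 0; SD of change 1.5 to 3.5 for VAS and 8 to 18 for ODI; correlation between the three changes 0 to 0.9.

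**1. One scale, judged per subject.** The chance of being unchanged or better is 50% plus half the ties, which is Φ((step/2)/SD).

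| Scale | Formula | SD of change | Met with no true change |
|---|---|---|---|
| VAS, whole points | Φ(0.5/SD) | 1.5, 2.5, 3.5 | 63%, 58%, 56% |
| VAS, read to 0.1 | Φ(0.05/SD) | 1.5, 2.5, 3.5 | 51%, 51%, 51% |
| ODI, steps of 2 | Φ(1/SD) | 8, 12, 18 | 55%, 53%, 52% |

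For example, Φ(0.5/1.5) = Φ(0.333) = 0.631. Whole-point VAS with an SD of only 1 gives Φ(0.5) = 69%, the highest value considered.

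**2. Scales combined.** A simulation of 1,000,000 draws used a change SD of 2.5 for each VAS and 12 for ODI. Ranges are over correlations 0 to 0.9; ties arise from whole-point VAS and 2-point ODI.

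| Rule | No ties | With ties |
|---|---|---|
| All three scales maintained | 12% to 39% | 18% to 45% |
| Back VAS and ODI maintained | 25% to 43% | 31% to 48% |
| Any one of three maintained | 61% to 88% | 67% to 92% |

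As an analytic check at correlation 0.5 without ties, the all-three rate is 1/8 + 3·arcsin(0.5)/(4π) = 1/8 + 1/8 = 25%, which matches the simulation.

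**3. Regression to the mean.** Suppose subjects enrol 1 SD above their usual level, with test-retest reliability r. The chance of a lower score later is Φ((1−r)/√(1−r²)). For r = 0.7, 0.8 and 0.9 this is Φ(0.420), Φ(0.333) and Φ(0.229), or 66%, 63% and 59%, with no treatment effect.

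**4. Does mean change avoid this?** No. With r = 0.7 the expected spurious improvement is 1 − 0.7 = 0.30 SD, and the conditional SD is √(1 − 0.49) = 0.71. At an assumed N of 50, z = 0.30/(0.71/√50), about 3, so a 95% CI for the mean change would usually exclude zero without any surgical benefit.

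**5. Could a high proportion still be informative?** Take an assumed N of 50 and a no-change rate of 58%. An exact binomial test excludes that rate at 37/50 or more (one-sided alpha 0.014). Power is 98% if the true rate is 84%, which is Φ(1), the rate without ties for a mean improvement of 1 SD.

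**The case against.** The strongest reply is that section 4.6.2 is too loosely worded to be attacked as a rule. It names no unit and joins pain and disability with *and*, which can be read as requiring all scales. Scores are collected at every visit, and nothing in section 5 confines reporting to a percentage or prevents reporting the size of the change. All of this stands. It changes the diagnosis to an under-specified criterion that also credits no change; it does not make crediting no change sensible.

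A reader might infer that more than half of subjects would succeed with no benefit. The documents do not support that as a general statement. It needs a per-subject, per-scale rule or an any-scale rule, and section 4.6.2 states neither. It fails in every all-scales case computed, and under a group-mean reading there is no subject rate at all. The higher VAS figures also need whole-point recording, which section 4.1.3 does not specify.

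A reader might also infer that the secondary result cannot show that surgery helped. That is too strong as a criticism of this criterion: step 5 shows that a proportion well above the no-change rate could establish improvement from baseline. Attribution to surgery is limited by the single-arm design, and step 4 shows that a better summary measure does not cure that.

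On leg pain, the documents do not say that unaffected subjects are recorded as 0, or how many there will be. Dropping them altogether would also hide new postoperative leg pain.

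**Conclusion.** The point holds as a defect of a secondary criterion. Whether applied to subjects or means, singly or combined, section 4.6.2 treats no change as favourable, against the expectation in section 2.1 and in a population selected after failed conservative care. Nothing elsewhere in the plan corrects it.

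Its size depends on definitions that the plan omits. Judged per subject and per scale, roughly 51% to 63% meet the criterion with zero true mean change, and up to 69% at the extreme of whole-point VAS with an SD of 1. An all-scales rule gives less than half in the cases computed, and an any-scale rule gives more. These figures rest on normal changes and assumed SDs, correlations and recording steps. The primary CT fusion outcome is unaffected.

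**What to change.** Replace the criterion in section 4.6.2 and add the analysis to section 5:

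- Report mean change from baseline to 12 months for ODI, VAS back and VAS leg, each with a 95% CI. Twelve months is the last visit that is not optional.
- Tabulate improved, unchanged and worse separately for each scale. If a responder rate is wanted, fix and justify its margin before data review.
- Report leg-pain improvement among subjects with leg pain at baseline, and new or worse leg pain separately for all subjects.
- Describe results as change from baseline after the combined procedure, and state that, without a control, regression to the mean and natural course cannot be separated from a surgical effect.

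The cost is protocol and SAP wording; no new data are needed. The reported result may look less favourable than a maintained-or-improved percentage.
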